6.1.10 Supportive analysis

Commercially Confidential Information

Variable and analysis set

For analysis 1 the combined APACHE II score as for the primary analysis will be used. This analysis will be run on the PD analysis set.

For analyses 2-4 mentioned above all available APACHE II scores at all scheduled visits (excluding discharge or early discharge visits) up to Day 29 after applying the rules for missing data and handling of discharge and death. These analyses will be based on the safety analysis set.

For the subgroup analyses the “PD analysis set” is used. In addition only participants in the high baseline CRP group are considered. The high baseline CRP group is defined as any subject with a baseline CRP value > median baseline CRP value of all participants in this study.

Commercially Confidential Information

Model checking procedures

The appropriateness of the normality assumption of the APACHE II scores will be assessed by graphical mean e.g. residual plots.

Graphical presentation of results

Estimated mean APACHE II scores +/- SE will be plotted over time by treatment group.

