6.1.3 Treatment arms/group

Participants will be assigned at randomization to one of the following treatment arms/groups in a ratio of 1:1:

- MAS825 CCI i.v.
- Matching placebo i.v.

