12.9 Sample size calculation

12.9.1 Primary endpoint(s)

The sample size is limited to maximum of 60 participants to be treated with a single i.v.dose of MAS825 due to limitations in the available drug supply at this point in time. To establish clinical efficacy based on APACHE II score a sample size of 60 participants per treatment group provides 80% power when testing on an 10% 1-sided alpha level under the assumption that MAS825 reduces the APACHE II score by 3.6 points more than placebo (assumed standard deviation of 9.2 based on [Yang et al 2020](#)).

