6.1.8 Handling of discharge and death

For the APACHE II score,

- in case a participant is discharged before Day 29 it will not be derived for any visits after the discharge visit (i.e. the last APACHE II score will be derived on the day of discharge).
- In case a participant dies no APACHE II score will be derived starting from the day of death.

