6.1.9 Derivation of the primary estimand

The primary estimand, referred to as the “**combined APACHE II score**”, will be derived as follows from the APACHE II scores after application of the missing data as well as discharge and death handling approaches described above:

- For participants hospitalized at Day 15: APACHE II score at Day 15
- For participants discharged prior to Day 15: APACHE II score at the discharge visit is used

- For participants that died on Day 15 or earlier: highest observed APACHE II score of any of the participants at any time during the trial.
- Imputation for death takes precedence over the imputation of the APACHE II score on day of early discharge.

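### Supportive APACHE II analyses 2-4 use only participants alive and in hospital, so they do not address the primary estimand and could shrink or reverse a survival benefit

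*SAP*

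**What the plan says.** The primary endpoint is a composite. SAP 6.1.9 assigns the following: "For participants that died on Day 15 or earlier: highest observed APACHE II score of any of the participants at any time during the trial". Participants discharged before Day 15 keep their discharge-visit score, those in hospital at Day 15 contribute that day's score, and death overrides discharge. Supportive analysis 1 (SAP 6.1.10) uses the same variable.

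Analyses 2-4 do not. Their data are defined thus: "For analyses 2-4 mentioned above all available APACHE II scores at all scheduled visits (excluding discharge or early discharge visits) up to Day 29", on the safety set, after the missing-data rules and the discharge and death rules. Under SAP 6.1.8, "In case a participant dies no APACHE II score will be derived starting from the day of death", and no score is derived for visits after the discharge visit. The carry-forward rule in SAP 6.1.7 cannot refill these visits, because it needs at least one APACHE II parameter reported at the visit. The output is described as follows: "Estimated mean APACHE II scores +/- SE will be plotted over time by treatment group".

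For the 9-point ordinal scale the SAP does the opposite: SAP 6.2.1 imputes the death score through Day 29 and carries the last value forward after discharge.

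**The concern.** Death and discharge are outcomes that treatment may change. Dropping both leaves, at each visit, two groups selected after randomisation. A participant whom MAS825 keeps alive but very ill adds a high score to the MAS825 mean, while the comparable placebo participant who died adds nothing at that visit. The visible text names no strategy for death or discharge in analyses 2-4 and gives no caution about reading the plotted means.

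At stake is interpretation. Analyses presented as support for the primary result could point away from it for a reason unrelated to lack of benefit.

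**Working it through.** Differences are MAS825 minus placebo; negative favours MAS825.

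**The plan's own figure.** Protocol 12.9.1 states that "a sample size of 60 participants per treatment group provides 80% power when testing on an 10% 1-sided alpha level", assuming that "MAS825 reduces the APACHE II score by 3.6 points more than placebo" and an "assumed standard deviation of 9.2". Allocation is 1:1 (Protocol 6.1.3). The standard error is 9.2 × √(2/60) = 1.680, and 3.6/1.680 = 2.143. Subtracting the one-sided 10% critical value of 1.282 leaves about 0.86, so power is 80.6% (80.4% with the noncentral t). The stated 80% reproduces. It concerns the primary comparison; the documents give no corresponding figure for analyses 2-4 and no planning rates for death or discharge.

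**Day 15 mixture.** Assumptions, not in the documents:
- Placebo: 20% dead, 50% discharged at score 7, 30% in hospital at mean 14.
- Highest observed score W: 30 to 40.
- The drug moves a fraction s of patients (0.05 or 0.10) from dead to in hospital at score r, and changes nothing else.
- r is 18, the non-survivor median cited in Protocol 4.2, or 22 (assumed).

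Composite difference = s(r − W).

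In-hospital difference = (0.30 × 14 + s × r)/(0.30 + s) − 14 = s(r − 14)/(0.30 + s).

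| s | r | Composite, W = 30 | Composite, W = 40 | In hospital |
|---|---|---|---|---|
| 0.05 | 18 | −0.6 | −1.1 | 0.05 × 4/0.35 = +0.6 |
| 0.10 | 18 | −1.2 | −2.2 | 0.10 × 4/0.40 = +1.0 |
| 0.05 | 22 | −0.4 | −0.9 | 0.05 × 8/0.35 = +1.1 |
| 0.10 | 22 | −0.8 | −1.8 | 0.10 × 8/0.40 = +2.0 |

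Discharge only: if a further 10% leave (score 10 in hospital, 7 at discharge), the composite moves by 0.10 × (7 − 10) = −0.3. The in-hospital mean becomes (0.30 × 14 − 0.10 × 10)/0.20 = 16, a difference of +2.0.

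**Simulation.** This used 60 per arm, 200 trials per scenario and an assumed severity process: participants above an upper threshold may die and those below a lower one may be discharged. Three Day 15 estimates were compared, all adjusted for baseline but not for the stratification factors: ANCOVA on the composite, ANCOVA on in-hospital scores, and a likelihood MMRM with unstructured covariance on scheduled in-hospital scores to Day 15.

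| Scenario | Composite | In-hospital ANCOVA | MMRM | Composite favours drug, MMRM does not |
|---|---|---|---|---|
| No effect | −0.01 | +0.08 | +0.09 | 16% |
| Fewer deaths (19% to 10%) | −0.81 | +1.31 | +0.60 | 44% |
| Faster discharge (43% to 52%) | +0.21 | +1.08 | +0.84 | 20% |
| Both | −0.63 | +2.13 | +1.43 | 54% |
| Better severity slope only | −1.67 | −0.25 | −1.29 | 6% |

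With 200 trials, the simulation error of the 44% is √(0.44 × 0.56/200) = 3.5 percentage points. The MMRM borrows the earlier scores of those who later die or leave, so it in effect estimates scores as if nobody had. That softens the selection but still differs from the composite.

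**The case against.** The list of analyses 2-4 and their models are redacted. The SAP refers to estimated means and model checking, so these are probably not raw inpatient averages, and SAP 6.2.3 already uses an MMRM for CRP. If a similar model is used here, the raw calculation overstates the problem: in the fewer-deaths scenario the MMRM roughly halves the distortion (+0.60 against +1.31). This stands, and redacted mitigation cannot be excluded. The data rule itself is visible, however, and the MMRM did not restore the sign.

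The mixture also assumes no benefit to other inpatients. An improvement of s(r − 14)/0.30 points in them would cancel the raw reversal: from 0.05 × 4/0.30 = 0.7 to 0.10 × 8/0.30 = 2.7 points. This stands too; reversal is possible, not expected.

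Other displays would expose a difference in deaths or discharges. SAP 6.1.2 reports the frequency of death imputation by arm, summarises available discharge and Day 15 scores for early discharges, and marks both events on the individual plots. The ordinal scale has stacked bars and a heat map, survival without invasive ventilation has Kaplan-Meier curves, and deaths are tabulated. These help a careful reader but leave the plotted means unchanged.

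Finally, analyses 2-4 may legitimately ask a different question. If so, the SAP should state it; Protocol 12.4.7 lists no supportive analyses, so it supplies no purpose.

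**Conclusion.** The point holds as a limited one about supportive analyses. The means over time from analyses 2-4 are conditional on being alive and hospitalised and do not address the primary estimand. If MAS825 reduces deaths and those saved remain severely ill in hospital, these means can shrink or reverse the effect that the composite shows. Under the stated assumptions the raw in-hospital difference is about +0.6 to +2.0 points, against −0.4 to −2.2 for the composite.

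Three stronger readings are not supported:
- A reader might infer that an effective drug will generally look harmful. If it works by lowering severity, an MMRM mostly keeps the right sign (−1.29 against −1.67).
- A reader might infer that faster discharge alone would contradict the primary result. That depends on the scores at which patients leave: the mixture gives opposite signs (−0.3 and +2.0), but in the simulation the composite did not favour the drug either (+0.21).
- A reader might infer that the trial's conclusion is at risk. The primary test, its power and supportive analysis 1 all use the composite and are untouched.

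**What to change.** Add to SAP 6.1.10 a by-visit analysis and plot of the combined score, applying the SAP 6.1.9 rules at each scheduled visit to Day 29: carry the discharge score forward after discharge, assign the highest observed score from the day of death, and let death take precedence. Analyse each visit separately with the primary ANCOVA terms. Forcing constant post-death values into a normal repeated-measures model would strain its assumptions. On the safety set, the Day 15 result should equal the primary analysis, which gives a built-in programming check.

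Keep the existing in-hospital analyses as descriptive only. Label them as conditional on being alive and hospitalised, and show the numbers in hospital, discharged and dead per arm at each visit.

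The cost is SAP wording, one more derived variable and an additional output. The downside is more imputed points, including the same extreme value repeated after each death.

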6.2 Secondary objectives

6.2.1 Variables

The following variables and corresponding objectives are classified as secondary pharmacodynamic endpoints and will be evaluated for their effect of MAS825 compared with placebo,

- On inflammatory status: Serum C-reactive protein (CRP) levels and ferritin
- On clinical status: Endpoints based on the 9-point ordinal scale:
- Survival without the need for invasive mechanical ventilation at Days 15 and 29 defined by a 9-point ordinal scale score of < 6 points at all time points
- At least one level improvement in clinical status at Days 15 and 29: defined as difference of ≥ 1 in the 9-point ordinal scale score of the screening value – Day 15 or Day 29 respectively.
- Clinical status over time

Missing data

For the clinical status 9-point ordinal scale missing values will be handled as follows:

- For participants who died prior to Day 29: The score for death will be imputed for all visits following the death up to and including Day 29.

For all other participants: LOCF will be applied up to and including Day 127. Following discharge or early discharge LOCF will be applied to all intermediate visits.

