- As applicable, Pregnancy Outcomes Reporting Consent for female participants who took study treatment
 - Commercially Confidential Information
- As applicable, an optional Home Nursing visit consent for all participants to allow for home nursing visit if a site visit is not possible

Women of child-bearing potential must be informed that taking the study treatment may involve unknown risks to the fetus if pregnancy were to occur during the study and agree that in order to participate in the study they must adhere to the contraception requirements.

Commercially Confidential Information

A copy of the approved version of all consent forms must be provided to Novartis after IRB/IEC approval.

8 Visit schedule and assessments

The Assessment Schedule ([Table 8-1](#)) lists all assessments when they are performed. All data obtained from these assessments must be supported in the participant's source documentation.

Participants should be seen for all visits/assessments as outlined in the assessment schedule ([Table 8-1](#)) or as close to the designated day/time as possible. Missed or rescheduled visits should not lead to automatic discontinuation. Participants who prematurely discontinue the study for any reason should be scheduled for a visit as soon as possible, at which time all of the assessments listed for the final visit will be performed. If participant is prematurely discontinued from the study at any visit before Day 15, then assessments of Day 15 visit should be performed, and if participant is prematurely discontinued at any visit after Day 15 and before Day 127, then assessments of Day 127 visit should be performed.

Table 8-1 Assessment schedule

Period	Screening / Baseline / Treatment	Treatment ²									Post-Treatment Follow-up		EOS
Visit Name	Screening / Baseline / Treatment ¹⁴	Observation								Discharge ³	Follow-up ⁴ (if hospitalized assessments performed at site every 2 days; if discharged only telephone call on Day 29)	Safety follow-up ⁴	EOS/Safety Follow up ⁴
Days	-1 to 1	2	4	6	8	10	12	14	15	17, 19, 21, 23, 25, 27	29 (-1/+3 days)	45 ⁵ (+/-7 days)	127 (+/- 7 days) ⁵
Respiratory status (spont. breathing, FiO ₂ , ventilator parameters, ECMO), fluid balance, need for CRRT	X	X	X	X	X	X	X	X	X	X	X	X	X
APACHE II, CCI	X	X	X	X	X	X	X	X	X	X	X	X	X
Clinical Status Evaluation with 9-category ordinal scale	X	X	X	X	X	X	X	X	X	X	X	X	X
Weight and Height ⁷	X				X				X				
ECG evaluation (local) ¹⁴	X									X			

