12.5.2 Safety endpoints

For all safety analyses, the safety set will be used. All listings and tables will be presented by treatment group.

Safety summaries (tables, figures) include only data from the on-treatment period with the exception of baseline data which will also be summarized where appropriate (e.g. change from baseline summaries). In addition, a separate summary for death including on treatment and post treatment deaths will be provided. In particular, summary tables for adverse events (AEs) will summarize only on-treatment events, with a start date during the on-treatment period (treatment-emergent AEs).

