6.2.2 Descriptive analyses

CRP and ferritin

Panels of individual spaghetti plots over time for CRP and ferritin will be provided using a logscale. The profiles of all participants in the respective treatment group will be included in these graphs as grey lines in the background and the respective individual participants profile will be plotted with darker color in the foreground. The respective applicable normal ranges will be added and it will be indicated by a symbol if a patient died.

Survival without the need for invasive mechanical ventilation

The numbers and percentages of responders will be calculated up to Day 15 and up to Day 29 respectively. It will be presented by treatment group together with the difference in response rates.

Improvement in clinical status

The numbers and percentages of responders will be calculated up to Day 15 and up to Day 29 respectively. It will be presented by treatment group together with the difference in response rates and a two-sided 90% CI based on Fishers exact test.

In addition a shift table of changes in response status will be provided with weekly time intervals (e.g. baseline, week 1, week 2, week 3 and week 4). For this the following response categories will be included:

- improvement of at least 1 step from baseline,
- no change from baseline
- worsening from baseline.

Also a stacked barchart illustrating the percentage of participants in each response categories as outlined above will be provided. Treatment groups will be presented next to each other. This will be provided for weeks 1, 2, 3 and 4.

For the subgroup analysis a shift table and stacked barchart for subgroup of participants with high baseline CRP by high and low corticosteroid dose during week 1 will be provided.

Clinical status over time

The 9-point ordinal scale will be summarized (mean, median, standard deviation, minimum, maximum, frequencies and percentages in each category) will be summarized by visit (including a time point for data from early discharge) and treatment group.

A stacked barchart illustrating the percentage of participants for each category of the 9-point ordinal scale with one bar will be provided. Treatment groups will be presented next to each other within one category. This will be provided for Day 8, Day 15, Day 21 and Day 29 (labeled as weeks 1, 2, 3 and 4).

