7.2.6 Adverse events

All information obtained on adverse events will be listed by treatment and subject.

Summary tables for adverse events (AEs) will summarize only on-treatment events, with a start date during the on-treatment period (treatment-emergent AEs).

The number and percentage of subjects with adverse events will be tabulated by body system and preferred term with a breakdown by treatment. Separate summaries will be provided for study medication related adverse events and other significant adverse events leading to discontinuation.

The number of deaths resulting from SAEs suspected to be related to study treatment and SAEs irrespective of study treatment relationship will be provided by SOC and PT until day 29 and after day 29.

The number of deaths resulting from SAEs suspected to be related to study treatment and SAEs irrespective of study treatment relationship will be provided by PT until day 29 and after day 29.

A subject with multiple adverse events within a body system is only counted once towards the total of this body system and treatment.

For the legal requirements of ClinicalTrials.gov and EudraCT, two tables are required:

on treatment emergent adverse events which are not serious adverse events and on treatment emergent serious adverse events and SAE suspected to be related to study treatment will be provided by system organ class and preferred term on the safety analysis set.

If for a same patient, several consecutive AEs (irrespective of study treatment causality, seriousness and severity) occurred with the same SOC and PT:

- a single occurrence will be counted if there is ≤ 1 day gap between the end date of the preceding AE and the start date of the consecutive AE
- more than one occurrence will be counted if there is > 1 day gap between the end date of the preceding AE and the start date of the consecutive AE.

For occurrence, the presence of at least one SAE / SAE suspected to be related to study treatment / non SAE has to be checked in a block e.g., among AE's in a ≤ 1 day gap block, if at least one SAE is occurring, then one occurrence is calculated for that SAE.

The SAEs and deaths by State will be graphically presented in a barchart. Refer to [Section 10.8](#) for details on the state.

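### The death rule for the 9-point scale stops at Day 29 while LOCF runs to Day 127, so a death on or after Day 29 with no recorded 8 can be carried as alive, and earlier deaths have no stated value at Days 45 and 127

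*SAP*

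**What the plan says.** SAP 6.2.1 (Missing data) has two main rules for missing values on the 9-point scale. The first covers participants who died before Day 29: "The score for death will be imputed for all visits following the death up to and including Day 29". The second reads: "For all other participants: LOCF will be applied up to and including Day 127". A further sentence applies LOCF to the intermediate visits after discharge.

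The scale is due beyond Day 29. Protocol Table 8-1 has a row "Clinical Status Evaluation with 9-category ordinal scale" that is marked at every visit, including Days 45 and 127. SAP 6.2.2 says that the scale "will be summarized by visit (including a time point for data from early discharge) and treatment group", with no Day 29 limit. The bar chart, weekly shift tables and heat map stop at Day 29 or week 4. Clinical status over time is a listed secondary endpoint in both documents.

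On recording, Protocol 8.3.3 scores each day by its worst status. It asks for the scale by phone at the scheduled visits after discharge, and for a status on Day 127 or the day of discharge.

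**The concern.** The two rules divide participants by whether death came before Day 29, not by whether they died. Anyone who dies on or after Day 29 therefore belongs to the LOCF group. If no 8 was entered, the last score from when the participant was alive fills the visits after death. The death score and LOCF also end at different visits, Day 29 and Day 127, so participants who died early have no rule after Day 29.

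At stake is a by-visit table for a secondary endpoint that could show dead participants in a living category, or leave their category to the programmer. That table could then disagree with the planned death tables.

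**Working it through.** The plan gives no figure for this point, so there is none to reproduce. The check applies the rule to example deaths and then sizes one misplaced participant.

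**Inputs**
- Death score 8; alive scores 0 to 7 (Protocol Appendix 2, SAP 10.6).
- 60 participants per arm (Protocol 4.2 and 12.9.1). I assume that all 60 are in the table.
- Days 29, 45 and 127 (Protocol Table 8-1), taken here on their nominal days.
- Assumption for illustration: the last alive score is 6 and no 8 was recorded.

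**Step 1. The literal rule against a rule based on the date of death**

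| Day of death | SAP rule: Day 29 / 45 / 127 | Date-of-death rule: Day 29 / 45 / 127 |
|---|---|---|
| 10 or 28 | 8 / none stated / none stated | 8 / 8 / 8 |
| 29 | 6 / 6 / 6 | 8 / 8 / 8 |
| 40 | 6 (alive) / 6 / 6 | 6 (alive) / 8 / 8 |
| 100 | 6 (alive) / 6 (alive) / 6 | 6 (alive) / 6 (alive) / 8 |

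For deaths on or after Day 29, a recorded 8 removes the difference, because LOCF then carries the 8. It does not settle the first row. Those participants are outside the LOCF group, so even a recorded 8 has no stated carry-forward past Day 29.

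**Step 2. Size of one late death carried as alive**
- Category 8 at the affected visit: 1/60 = 1.7 percentage points too low.
- For an assumed 1, 2 or 3 such deaths in one arm, Day 127 is too low by 1/60 = 1.7, 2/60 = 3.3 or 3/60 = 5.0 points. Day 45 is too low by between 0 (all deaths after that visit) and the same figures (all before it).
- Mean score, with last alive score s: too low by (8 − s)/60. This is 1/60 = 0.017 for s = 7 and 7/60 = 0.117 for s = 1.
- If every late death has a recorded 8, all of these are 0.

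**Step 3. A death on Day 29**
- The Day 29 visit has a window of −1/+3 days. A participant assessed alive on Day 28 has an observed value and nothing is imputed. The problem needs no observed visit and no recorded 8.
- Survival without invasive ventilation is defined by a "9-point ordinal scale score of < 6 points at all time points". A participant with an earlier score of 6 or more has already failed, so the result changes only if no earlier score reached 6.
- Improvement needs the screening score minus the Day 29 score to be at least 1. A true 8 is never a response, since screening − 8 cannot be positive. The carried score gives a false response only if it is at least 1 below screening.
- Where its condition is met, one such death raises that response rate by 1/60 = 1.7 points.

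**The case against.** The strongest reply is that sites will record the death. Protocol 8.3.3 asks for the scale by phone after discharge and for a Day 127 status. Fatal events are SAEs reportable within 24 hours up to the last study visit (Protocol 10.1.2 and 10.1.3), so late deaths would be known. That makes an unrecorded 8 less likely, and a reader should not infer that every late death will be misclassified. Recording is still not assured. The phone-visit list in Table 8-1, footnotes 3 and 4, covers performance status and adverse events but does not name the scale, and the visible text does not tell sites to enter 8 on the date of death.

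It can also be said that the consequence is slight, and this stands. Days 45 and 127 are safety follow-up visits. The by-visit summary carries no test or confidence interval, and its use at those days is inferred from the absence of a limit and from LOCF running that far. Deaths also appear elsewhere: the Protocol promises that "a separate summary for death including on treatment and post treatment deaths will be provided", and under SAP 7.2.6 fatal SAEs "will be provided by SOC and PT until day 29 and after day 29". A reader could see the mismatch.

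The APACHE II rule is only a partial comparison. SAP 6.1.8 says: "In case a participant dies no APACHE II score will be derived starting from the day of death". It works from the day of death, but it stops derivation and assigns no score.

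Three stronger readings are tempting and not supported:
- That participants who died before Day 29 will drop out of the Day 127 table. The SAP is silent on them. It does not say to exclude them or to set them missing.
- That any Day 29 death distorts both Day 29 endpoints. Each changes only under its own condition in Step 3.
- That calendar days show how many late deaths would also affect Day 45. The documents give no timing of late deaths, and the Day 45 visit has a window of ±7 days.

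**Conclusion.** The point holds, as a minor one. As written, the rule gives a wrong value for a death after Day 29 with no recorded 8: at Day 127, and at Day 45 if death came before that visit. It can do the same at Day 29 for a death on that day, in rare cases. Separately, it leaves the Day 45 and Day 127 values undefined for deaths before Day 29, whatever was recorded. No visible passage overrides this.

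Each late death carried as alive costs 1.7 percentage points in category 8 at the affected visit, on the assumption of 60 participants per arm in the table. The total cannot be computed, because the documents give neither a rate of late death nor a rate of unrecorded scores. For deaths after Day 29, only the descriptive by-visit summary is exposed. The primary endpoint, the Day 15 endpoints and the safety death tables do not change.

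**What to change.** Replace the first two sentences of the missing-data rule in SAP 6.2.1 with:

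> For any participant who died, score 8 is assigned at every scheduled visit on or after the date of death, through Day 127. LOCF is applied through Day 127 to missing scores at visits before the date of death, and at all visits for participants not known to have died.

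Keep the sentence on intermediate visits after discharge, subject to the death rule. Where a visit did not take place, compare its nominal day with the date of death.

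This closes all three gaps. Day 15 results do not change, and Day 29 results change only for a Day 29 death with no recorded 8 and no observed visit. The cost is two SAP sentences and one line of derivation code. No new data are needed, since deaths are already collected and split at Day 29 for the tables in SAP 7.2.6.
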